
in a number of surgical settings. (2, 3) Liposomal bupivacaine is FDA approved for surgical infiltration, field blocks, fascial plane blocks of the abdomen, dental blocks, and interscalene brachial plexus blocks. A number of new abdominal wall block techniques have been developed over the last several years, and following some initial confusion related to the wording of the label, the FDA issued a clarification letter that stated that truncal fascial plane blocks such as the transversus abdominis plane (TAP) block are an on-label use of the medication (see attached clarification letter). The quadratus lumborum (QL) block is a type of TAP block, wherein local anesthetic is infiltrated into the fascial plane between muscles of the lateral abdominal wall.

Design & Procedures

This is a single center, observational prospective and retrospective cohort study.

Prospective: On the day of surgery, subjects will receive a QLB in the preoperative holding area as follows:

Subjects will be positioned in the right lateral decubitus position, and will be attached to standard ASA monitors (pulse oximetry, EKG, non-invasive blood pressure). Oxygen 5 L/min will be supplied via a face mask. Sedation/analgesia with midazolam 1- 2 mg IV and fentanyl 25- 100 mcg IV will be administered.

After appropriate skin preparation and draping, a 60 mm, 2-5 MHz curvilinear ultrasound transducer will be placed on the skin over the intercristal line (approximately L3/4 disc space) on the midline of the back. The transducer will be translated laterally to the left until the quadratus lumborum and psoas major muscles are identified. The transducer will then be rotated until the quadratus muscle is seen in its long axis, just below its attachment on the 12th rib.

A 21 gauge, 10 cm echogenic block needle (Pajunk Sonoplex, Norcross, GA) will then be inserted from the inferior aspect of the transducer and advanced until the tip is visualized in the fascial plane between the QL and psoas major muscles. Following negative aspiration for blood, 30 ml of injectate will be slowly administered with intermittent aspiration. Each 30 ml aliquot will contain 10 ml of liposomal bupivacaine (133 mg) and 20 ml of 0.25% bupivacaine (50 mg). The block will then be repeated on the right side.

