Following the block, subjects will proceed to the operating room where they will undergo a standard general anesthetic with endotracheal intubation (desflurane or isoflurane in a mixture of air/oxygen). The dosing of intraoperative opioids will be left to the discretion of the attending anesthesiologist in the room.

In the Post-Anesthesia Care Unit (PACU) and on the postoperative floor, subjects will have access to oxycodone 5-15 mg PO q3h prn for rescue analgesia (the primary outcome measure). In the PACU, patients will also have access to intravenous hydromorphone if the oral opioid

provides inadequate relief. Finally, subjects may receive a standard multimodal analgesia regimen consisting of:

- Acetaminophen 975 mg PO q6h (beginning in preop holding)
- Gabapentin 600 mg PO once in holding, then 100 mg PO tid thereafter
- Ketorolac 15 mg IV prior to skin closure

While this standard regimen is expected, it may vary per clinical care team judgement and/or preference. Any alterations in this standard regimen will not be considered a protocol deviation.

Assessments

Patient assessments will be performed or recorded by a research assistant twice daily (unless otherwise specified). Assessments made after discharge will be recorded by subjects who will be provided with a diary to document the outcomes. Outcomes to be measured include:

Opioid consumption. Cumulative opioid consumption over 48 hours is the primary outcome measure. Data will be drawn from PACU records and from the nursing medication records on a twice-daily basis. Post discharge opioid use will be tracked in the take-home patient diary. The patient will be called at 7 days after surgery to collect.

NRS-11. The 11-point Numeric Rating Scale (0-10) will be used as a secondary outcome measure. Two measures will be taken with each assessment, one at rest and one with coughing. These will be conducted preoperatively, 30 minutes after arrival to PACU, and at time points 8 hrs., 24 hrs., 36 hrs. 48 hrs, 72 hrs, 96 hrs., 120 hrs., 144 hrs. and 168 hrs.

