Historical data of 30 patients that meet inclusion criteria and meet no exclusion criteria, will be collected and for the retrospective group. The anesthesia statisticians will evaluate the following data from the patient's electronic medical record if available, including but not limited to hospital notes, anesthesia notes, medical history, medications, pain service notes, and flowsheets from admission to discharge. Electronic medical records will be used to assess the following items to compare to the prospective cohort.

Opioid consumption. Cumulative opioid consumption at 24hours, 48 hours and 72 hours. 48 hours is the primary outcome measure. Data will be drawn from PACU records and from the nursing medication records.

NRS-11. The 11-point Numeric Rating Scale (0-10) will be used as a secondary outcome measure. These will be collected from the preoperative assessment record, 30 minutes after arrival to PACU, and at time points 8 hrs., 24 hrs., 36 hrs. 48 hrs. and 72 hrs.

Thoracic epidural success and adverse events. Evidence of epidural block success/failure (as described in the anesthesia record and in daily Inpatient Pain Service notes). This will be done at the time of pain assessment (30 minutes after arrival to PACU, and at time points 8 hr, 24 hr, 36 hr and, 48 hr and 72 hr). Subject data will be collected for potential adverse events related to the epidural including evidence of hypotension, urinary retention, inability to ambulate per physical therapy. (known possible side-effect of thoracic epidural approach).

Hospital length of stay. Measured both by raw length of stay and by time to achieving "discharge readiness", defined by the presence of 3 criteria: a pain score of 3 or less with ambulation, no opioids required in the preceding 6 hours, and the ability to perform self-care (go to the toilet, dress, and shower).

Incidence of opioid-related adverse events. Incidence of nausea, vomiting, ileus, constipation, orthostasis, pruritis, urinary retention, respiratory depression

Time to first mobilization. Measured from time of arrival in PACU (time zero)

Cost. Hospital costs including pharmacy-related costs, costs due to opioid-related adverse events, the cost associated with nursing interventions and drugs to treat opioid-related adverse events, and overall hospital admission costs will be calculated.

Selection of Subjects

Criteria for inclusion in Prospective cohort:

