- Patients scheduled for elective, laparoscopic colonic resection by one of three surgeons: Drs. [name], [name] or [name]. These surgeons perform this procedure in the same manner
- Age 18-85 years
- American Society of Anesthesiologists (ASA) Physical Class I-III
- BMI 18-35 kg/m²

Criteria for exclusion in Prospective Cohort:

- Inability to consent
- Inability to speak English
- Pregnancy
- Emergency surgery
- Contraindications to regional blockade: coagulopathy or bleeding diathesis, local infection, allergy to local anesthetics
- Allergies/intolerances/contraindications to any of the multimodal agents (acetaminophen, gabapentin, ketorolac)
- Daily opioid equivalent use of 30 mg of morphine or greater at time of consent
- History of drug or alcohol abuse
- Uncontrolled anxiety, schizophrenia or other psychiatric disorder that, in the opinion of the investigator, may interfere with the study assessments of compliance.

Criteria for inclusion in Retrospective cohort:

- Patients that have had a laparoscopic colonic resection in the past year by Drs. [name], [name] or [name] and received thoracic epidural analgesia.
- Thoracic epidural analgesia must be placed in preoperatively, must be sited between levels T8 and T12, and must be started while the case is going- i.e. not started in PACU.
- Age 18- 85 at the time of the procedure.
- American Society fo Anesthesiologists (ASA) Physical class between I- III.
- BMI 18- 35 kg/m².

- Received the standard multimodal medication regimen for pain as outlined in the ERAS protocol for colorectal surgery

Criteria for exclusion in Retrospective cohort:

- Emergency surgery
- Daily opioid equivalent use of 30 mg of morphine or greater at time of consent.
- History of drug or alcohol abuse.
- Uncontrolled anxiety, schizophrenia or other psychiatric disorder.

Risk/Benefit Assessment

Risks of the study intervention relate to those associated with the quadratus lumborum block. These include routine risks of block procedures including bleeding, infection, nerve damage, local anesthetic systemic toxicity, as well as transient weakness of the hip flexor muscles (a known possible side-effect of QL block).

If subjects receive the quadratus lumborum block, they may experience improved pain control and/or reduced side effects compared to the epidural pain relief option, but it is not known yet whether this will be the case.

Data Analysis & Statistical Considerations

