We will use descriptive statistics (mean (SD) or frequency (%)) and group comparisons via Wilcoxon rank sum or fisher exact tests to measure differences between cohorts in opioid consumption, pain scores with rest and activity, and other secondary outcome measures.

Sample Size Justification

A difference in opioid consumption less than 20% would be considered non-inferior. Based on typical postoperative opioid consumption following laparoscopic colectomy (20mg +/- 5.2 mg), a total of 54 subjects (27 in each group) would be required to reject the null hypothesis that QL blockade is inferior in the first 48 hours with the study intervention, given an alpha of 0.05 and a power of 0.8. We plan on recruiting 45 subjects to account for dropout.

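### QLB patients qualify on the operation scheduled and TEA patients on the operation they have had, and neither cohort has a rule for conversion to open surgery

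*Combined protocol and SAP*

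**What the plan says.** The prospective inclusion criteria admit "Patients scheduled for elective, laparoscopic colonic resection by one of three surgeons". Design & Procedures puts the block before the operation: "On the day of surgery, subjects will receive a QLB in the preoperative holding area as follows". A QLB patient has therefore qualified and been treated before anyone can know whether the case will be completed laparoscopically.

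The retrospective inclusion criteria admit "Patients that have had a laparoscopic colonic resection in the past year by" the same surgeons, with an epidural placed preoperatively and started during the case. The chart review then takes "Historical data of 30 patients that meet inclusion criteria and meet no exclusion criteria", so that wording decides who enters.

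Conversion to open surgery does not appear in the document as a criterion, a reason for dropout, a recorded variable or an analysis rule. No analysis set is defined. The planned comparisons are unadjusted Wilcoxon rank sum and Fisher exact tests. The primary endpoint is stated as follows: "Cumulative opioid consumption over 48 hours is the primary outcome measure".

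**The concern.** One entry rule is fixed before incision and the other is worded by what has already happened. Conversion falls between the two. The Background attributes the pain of this operation largely to the small laparotomy through which the specimen is delivered, so incision size is part of the protocol's own account of pain. It is reasonable, though the documents do not show it, to expect a converted patient to need more opioid, mobilize later, stay longer and cost more.

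If converted cases enter only the QLB cohort, the contrast mixes the effect of the block with the effect of a larger operation. Under that assumption the bias runs against QLB. A true non-inferiority could be missed, and the comparisons of pain, mobilization, stay and cost would be distorted in the same direction.

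**Working it through.** **Inputs from the document (Sample Size Justification).** Margin: "A difference in opioid consumption less than 20% would be considered non-inferior". Mean and SD: "typical postoperative opioid consumption following laparoscopic colectomy (20mg +/- 5.2 mg" (20 mg, SD 5.2 mg). The margin is 0.20 × 20 = 4 mg. Alpha is 0.05, power 0.80, and 27 patients per group are required.

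**The plan's own figure.** n per group = 2 × 5.2² × (1.960 + 0.842)² / 4² = 26.5, rounded up to 27. This reproduces the stated figure, with alpha 0.05 two-sided (0.025 one-sided). At 27 per group the standard error is 5.2 × √(2/27) = 1.415, and power is Φ(4/1.415 − 1.960) = 0.81. The sample size arithmetic is not in dispute.

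**Inputs that must be assumed.** Let c be the proportion of scheduled cases converted and D the extra 48-hour opioid in a converted patient. The document gives neither. All rows below assume no true difference between block and epidural.

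**Formulas.**
- Mean shift if conversions enter QLB only: c × D.
- Variance in a cohort that contains conversions: V = 5.2² + c(1 − c)D².
- Power, conversions in QLB only: Φ((4 − cD) / √((5.2² + V)/27) − 1.960).
- Power, conversions in both cohorts at the same rate: Φ(4 / √(2V/27) − 1.960). The shift is then zero.
- Rank-based (Hodges-Lehmann) shift t, for normal data: solve (1 − c)Φ(t/s) + cΦ((t − D)/s) = 0.5, with s = 5.2√2 = 7.35.

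**Worked example, c = 10%, D = 10 mg.** The shift is 1.0 mg. V = 27.04 + 0.09 × 100 = 36.04.
- QLB only: the standard error is √(63.08/27) = 1.528, and power is Φ(3/1.528 − 1.960) = 0.50.
- Both cohorts: the standard error is √(72.08/27) = 1.634, and power is Φ(4/1.634 − 1.960) = 0.69.

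| c, D | Mean shift (share of 4 mg) | Rank-based shift | Power, QLB only | Power, both cohorts |
|---|---|---|---|---|
| 5%, +5 mg | 0.25 mg (6%) | 0.23 mg | 0.75 | 0.79 |
| 10%, +10 mg | 1.0 mg (25%) | 0.81 mg | 0.50 | 0.69 |
| 15%, +20 mg | 3.0 mg (75%) | 1.62 mg | 0.07 | 0.38 |

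**On the planned test.** The power columns compare means, but the plan uses a rank test and does not say how the margin enters it. I simulated a margin-shifted Wilcoxon test with 27 QLB and 30 TEA patients and normal data. Power is about 0.79 with no conversions. With D = 20 mg and conversions in QLB only, it is about 0.61 at 5% and 0.26 at 15%. The average Hodges-Lehmann estimate at 15% is about 1.7 mg. The rank test softens the effect but does not remove it.

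In 27 patients these conversion rates mean about 1 to 4 people (27 × 0.05 = 1.4; 27 × 0.15 = 4.1).

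**The case against.** The document is silent on conversion, so neither half of the imbalance is recorded as fact. The past tense in the TEA criterion may be no more than what a retrospective criterion needs. It does not require completion by laparoscopy, no search method is described, and a converted case could be counted as laparoscopic. A converted QLB patient might be put under the unspecified dropout allowance. All of this stands. If both of those readings were followed, the imbalance would reverse. This shows why a stated rule is needed, but it also means that the literal reading is only what the criteria allow.

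A reader might infer four stronger things that the documents do not support:

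- **That conversions are in fact kept in QLB and removed from TEA.** Only the wording points that way.
- **That most of the margin is used up.** That needs the largest assumed inputs and the scale of means. The smallest case uses 6% of the margin, and the planned rank test responds less to a few high values.
- **That the problem cannot be repaired at analysis.** Restricting both cohorts to operations completed laparoscopically removes this imbalance, provided that conversion is recorded.
- **That every secondary outcome is affected.** Sleep quality and satisfaction are listed only for the prospective cohort and have no TEA contrast.

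The direction also limits the harm. Under the literal reading, and if conversion raises opioid use, the bias works against the study's hypothesis and would not create a false claim of non-inferiority.

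**Conclusion.** The concern holds as a flaw in the stated entry rules: the two cohorts are anchored on opposite sides of an intraoperative event, and nothing in the plan corrects this. What is certain is the difference in wording and the absence of any conversion rule. The bias against QLB depends on the criteria being applied literally and on converted patients using more opioid.

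Its size cannot be set from the documents. The illustrated range runs from negligible to most of the margin on the mean scale and to about two fifths of it on the rank scale (1.62/4 = 41%). The change should be made because the rule is cheap to align and the possible effect on a 4 mg margin is not trivial.

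**What to change.** Use one anchor for both cohorts. Reword the retrospective criterion to patients scheduled (booked) for elective laparoscopic colonic resection by the same three surgeons, identified from the booked procedure or the preoperative notes, and state that converted cases are included. The TEA criteria already require an epidural placed before surgery, so this anchor fits that cohort too. Record conversion to open surgery in both cohorts from the operative record. Add a sensitivity analysis restricted to operations completed laparoscopically in both cohorts.

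The document does not show that booking data are retrievable. If they are not, make restriction to laparoscopically completed cases the stated rule for both cohorts.

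The cost is a somewhat different chart search and one extra recorded variable, with no increase in the planned numbers. Converted cases in both cohorts add variability and lower power, for example from 0.81 to about 0.69 at 10% conversion with 10 mg extra. That is still better than the 0.50 when they enter QLB only, and the comparison is then free of this bias. With larger assumed inputs the loss is greater (0.38 at 15% with 20 mg extra), which is why the sensitivity analysis should be prespecified.

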Laparoscopic colectomy is a surgical procedure that is primarily performed for resection of a GI malignancy. While most of the procedure is performed via laparoscopic ports in the anterior abdominal wall, the resected specimen is typically delivered through a small lower abdominal laparotomy, which results in a moderately severe burden of pain for these patients. Enhanced recovery after surgery (ERAS) protocols are aimed at improved return to function with minimal disruption in the functional capacity, and have been shown to reduce hospital length of stay, complications, and costs. One standard therapeutic component of the ERAS program at Duke for colorectal surgery is thoracic epidural analgesia (TEA), which is typically maintained for 2 days postoperatively. While TEA usually provides high-quality analgesia of the abdomen, drawbacks include technical difficulties with insertion, patchy or non-functioning block, pruritis and/or urinary retention due to epidural opioids, impairment of mobility due to leg weakness or the presence of a pump apparatus on an IV pole, and most importantly, associated hypotension which often results in the epidural local anesthetic infusion being discontinued. Alternatives to TEA include infiltrative blocks of the wall of the abdomen. The quadratus lumborum block (QLB) is a novel, ultrasound-guided infiltration technique whereby local anesthetic is deposited in the fascial plane between the quadratus lumborum and psoas major muscles at the level of L3-4.(1) Performed bilaterally, the QLB has been shown to provide a dermatomal block of the entire anterior abdominal wall. This may be the principal advantage of QLB over transversus abdominis plane (TAP) block, which is often patchy and restricted to a smaller area of the abdominal wall. In our institution, QLB is replacing TAP blockade for many abdominal procedures that have both upper and lower incisions or port sites. The QLB appears (both in the scant literature to date and in our institutional experience) to be reliable and technically simpler to perform than TAP blocks, as the needle is not moved once the fascial plane is breached. We wish to compare the effectiveness of QL blocks for postoperative analgesia in this population with a historical cohort that received thoracic epidural analgesia. Based on our experience, we believe that infiltrating this space with an admixture of bupivacaine and liposomal bupivacaine will result in excellent pain relief for an extended duration of time. Liposomal bupivacaine (Exparel®) is a slow-release, long-acting form of bupivacaine that has been shown to provide extended duration of analgesia and opioid sparing

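### QLB patients need not be suitable for, or willing to have, an epidural, whereas every TEA patient received one, so non-candidates for TEA may enter the QLB cohort only

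*Combined protocol and SAP*

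**What the plan says.** Design & Procedures describes the study thus: "This is a single center, observational prospective and retrospective cohort study".

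Under Selection of Subjects, the two cohorts are entered by different routes.

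- **Prospective (QLB).** Entry is open to "Patients scheduled for elective, laparoscopic colonic resection by one of three surgeons", within limits on age, ASA class and BMI. The one exclusion that bears on the choice of block is "Contraindications to regional blockade: coagulopathy or bleeding diathesis, local infection, allergy to local anesthetics". Nothing asks whether the patient could have had a thoracic epidural, was offered one, or would have accepted one.
- **Retrospective (TEA).** Patients must have had the same operation by the same surgeons in the past year "and received thoracic epidural analgesia". The epidural must have been placed before surgery, and it "must be sited between levels T8 and T12, and must be started while the case is going- i.e. not started in PACU".

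Data Analysis & Statistical Considerations plans "group comparisons via Wilcoxon rank sum or fisher exact tests to measure differences between cohorts in opioid consumption", and the same tests for pain scores and other secondary outcomes. It describes no matching, propensity score or covariate adjustment. The Sample Size Justification sets the criterion for the primary outcome: "A difference in opioid consumption less than 20% would be considered non-inferior".

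**The concern.** The study sets QLB against TEA, which Background & Significance presents as a standard part of the site's colorectal ERAS program. The contrast is easiest to interpret in patients who could have had either technique. Entry to the TEA cohort depends on having had an epidural sited and started on schedule, so each of those patients was in practice both suitable and willing. Entry to the QLB cohort carries no such condition.

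The protocol itself lists technical difficulty with insertion among the drawbacks of TEA. A patient in whom an epidural could not be sited cannot meet the retrospective criteria, while a similar patient can enter the QLB cohort.

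If patients who cannot or will not have an epidural differ in opioid use or mobilization, the difference between cohorts partly reflects who was admitted and not only which block was given. With no randomisation and no adjustment, nothing later in the plan would remove that part.

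**Working it through.** **1. Eligibility side by side.**

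| Question | QLB cohort | TEA cohort |
|---|---|---|
| Bleeding disorder, local infection, local-anesthetic allergy | Excluded by name | Not listed, but every patient did receive an epidural |
| Other bar to an epidural | Not addressed | Not listed, but every patient did receive an epidural |
| Patient declines an epidural | Not addressed | Cannot be in the cohort |
| Epidural could not be sited | Not applicable to entry | Cannot be in the cohort |

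The asymmetry lies in the last three rows. The first row is largely closed.

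**2. The plan's own sample size.** Inputs from the Sample Size Justification: mean 20 mg, SD 5.2 mg (reading the ± figure as an SD), margin 20%, alpha 0.05, power 0.8.

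- Margin = 0.20 × 20 = 4 mg.
- n per group = 2 × (1.960 + 0.842)² × 5.2² / 4² = 26.5, rounded up to 27, or 54 in total. This matches the plan, with alpha taken as one-sided 0.025. One-sided 0.05 gives 21 per group and does not match.
- Standard error of the difference = 5.2 × √(2/27) = 1.415 mg.
- Power at no true difference = Φ(4/1.415 − 1.96) = 0.807.

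**3. Illustration of size.** The documents give neither the share of non-candidates nor their opioid use, so both are assumptions. Let a share f of QLB patients be non-candidates whose mean 48-hour use differs by d mg. The QLB mean then shifts by b = f × d.

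- If they use more: power = Φ((4 − b)/1.415 − 1.96).
- If they use less: one-sided type I error at a true difference of 4 mg = Φ(b/1.415 − 1.96).

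| f | d (mg) | b (mg) | b as % of margin | Power if they use more | Type I error if they use less |
|---|---|---|---|---|---|
| 0 | – | 0 | 0 | 0.807 | 0.025 |
| 5% | 2 | 0.1 | 2.5 | 0.787 | 0.029 |
| 10% | 4 | 0.4 | 10 | 0.720 | 0.047 |
| 20% | 4 | 0.8 | 20 | 0.618 | 0.082 |
| 20% | 6 | 1.2 | 30 | 0.507 | 0.133 |

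These are normal approximations for means with the SD held at 5.2 mg and 27 per group. They follow the framework of the sample-size section, not the Wilcoxon test itself.

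**The case against.** Several counter-arguments have force.

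- **The exclusion is worded for regional blockade in general.** An epidural can be read as falling under that term, and the three named items would bar an epidural as well as a QLB. This stands: only a residual group is at issue. It does not cover that group fully, because the term is spelled out as three items and declining an epidural is not a contraindication.
- **The documents permit such patients but do not show any.** This stands. TEA is a standard component at the site, and nothing suggests that many patients cannot have it.
- **The stated population is laparoscopic colectomy patients, not those who could have had either block.** True, but a comparison with a cohort defined by receipt of TEA still needs comparable patients if the difference is to be attributed to the block.
- **Shared criteria limit the extremes.** Both cohorts exclude daily opioid use of 30 mg morphine equivalent or more, drug or alcohol abuse, and specified psychiatric conditions. This reduces the likely size of any difference but does not remove it.

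Three stronger readings are tempting and are not supported.

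- A reader might infer that the bias runs against QLB, because non-candidates might have more chronic pain. The documents give no basis for a direction.
- A reader might infer that covariate adjustment could not help, because such patients have no TEA counterpart. A history such as previous spinal surgery is not an exclusion for the retrospective cohort, so a patient with that history who received TEA can be in it.
- A reader might assume a larger difference, such as 10 mg, which at 10-20% of patients would move the mean by 1-2 mg, a quarter to half of the margin. Ten mg is half the planned mean and 10/5.2 = 1.9 SD, and nothing in the documents supports it.

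**Conclusion.** The point holds in a limited form. Eligibility is asymmetric: receipt of an epidural is required in one cohort, and neither suitability nor willingness is required in the other. The planned analysis does nothing to correct for this. The general exclusion for contraindications to regional blockade narrows the gap but does not close it.

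Whether any non-candidates enter, how many, and in which direction they would move the result are all unknown. Under the assumed ranges (5-20% of QLB patients, 2-6 mg), the effect runs from negligible to 30% of the margin. It would cost power in one direction and inflate the risk of a false non-inferiority conclusion in the other. It is one part of the wider question of comparability between a prospective and a historical cohort, and is worth acting on mainly because the remedy is cheap and specific.

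**What to change.** - **Patients still to be enrolled.** Add a prospective inclusion criterion that the patient would otherwise be eligible for, and would accept, TEA under the ERAS program. Record candidacy and the reason for any non-candidacy at enrolment, before the block is given.
- **Patients already enrolled.** Classify candidacy from the preoperative anesthesia note where available, by someone unaware of outcomes. Report the comparison limited to candidates as a sensitivity analysis, and state how many could not be classified. Because the notes may not record candidacy, this classification should not define the primary comparison.
- **Reporting.** Give the number of non-candidates, so that the assumed share is replaced by a measured one.

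**Cost.** One criterion and one recorded item. The eligible pool becomes smaller, and the result says less about patients who cannot have an epidural. The target of 27 per group need not change unless the restriction leaves fewer than 27 evaluable QLB patients. If the planned 45 refers to the QLB cohort alone, which the plan does not state, 45 − 27 = 18 patients (40%) could be lost to dropout and restriction together before that happens.

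**Limit.** The criterion addresses suitability and willingness. It does not make QLB patients comparable on whether an attempted epidural could have been sited, so that part of the selection should be acknowledged in the report.

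### The exclusion criteria are not the same for the QLB and TEA cohorts (psychiatric wording, language, consent), and the planned unadjusted comparison does nothing to offset this

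*Combined protocol and SAP*

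**What the plan says.** Selection of Subjects in the combined protocol and SAP sets out separate criteria for the two cohorts. Age, ASA class and BMI limits match. So, in substance, do the exclusions for emergency surgery, daily opioid use of 30 mg morphine equivalent or more, and a history of drug or alcohol abuse.

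The psychiatric lines differ. For QLB the exclusion is "Uncontrolled anxiety, schizophrenia or other psychiatric disorder that, in the opinion of the investigator, may interfere with the study assessments of compliance". For TEA it is "Uncontrolled anxiety, schizophrenia or other psychiatric disorder", with no further condition.

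Other exclusions appear on the QLB list only: "Inability to consent", "Inability to speak English", pregnancy, contraindications to regional blockade, and allergy, intolerance or contraindication to the multimodal agents. The TEA inclusion criteria instead require a preoperatively placed thoracic epidural and "Received the standard multimodal medication regimen for pain as outlined in the ERAS protocol for colorectal surgery".

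The opioid-use exclusion is dated to consent in both lists. Data Analysis & Statistical Considerations plans descriptive statistics with Wilcoxon rank sum and Fisher exact tests between cohorts. No matching or covariate adjustment is described.

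**The concern.** In a comparison with a historical cohort, eligibility is one of the few design tools that make the groups alike. Here the lists can treat the same patient differently. On a literal reading, a patient with a charted psychiatric diagnosis that would not disturb the study could be enrolled for QLB yet dropped from TEA. A patient who does not speak English could enter the TEA cohort but not the QLB cohort.

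Two features make this more than a matter of style. First, the primary analysis is unadjusted, so nothing later compensates for a difference in who was eligible. Second, TEA patients are found after their operation, when 48-hour opioid use is already in the record. A criterion that can be read two ways then leaves a chart screener a choice that could be made with the outcome in view.

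At stake is the non-inferiority conclusion. Its margin is 20%, or 4 mg on the 20 mg reference, so a selection shift of 1 mg would use a quarter of it.

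**Working it through.** **1. The lists side by side**

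| Item | QLB (prospective) | TEA (retrospective) |
|---|---|---|
| Psychiatric disorder | Limited by investigator judgement of interference | No such limit |
| Cannot consent | Excluded | Not listed |
| Does not speak English | Excluded | Not listed |
| Pregnancy | Excluded | Not listed |
| Block contraindication | Excluded | Not listed; largely implied, since an epidural had to be given |
| Multimodal-agent contraindication | Excluded | Not listed; largely implied, since the regimen had to be received |
| Opioid-use limit | Dated to consent | Dated to consent; no consent point described for chart review |

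The mismatches not covered elsewhere that could bear on the comparison are the psychiatric wording, language, capacity to consent and the opioid-use date. Pregnancy also differs, but no effect on the comparison is evident.

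**2. The plan's own sample size**

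Inputs from Sample Size Justification: margin 0.20 × 20 = 4 mg, SD 5.2 mg, alpha 0.05, power 0.8. With one-sided 0.025 and a true difference of 0:

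n per group = 2 × (1.960 + 0.842)² × 5.2² / 4² = 26.5, rounded up to 27, or 54 in total.

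This matches the plan. One-sided 0.05 gives 21 per group (42) and does not. The sample-size figure is not affected by this point.

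**3. Illustration for the psychiatric item only**

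The documents give no prevalence or effect, so both are assumed. Let p be the share of otherwise eligible patients with a charted, non-interfering disorder and r their opioid use relative to the rest. If all are removed from TEA and all kept in QLB, the TEA mean falls by the fraction p(r−1) / [1 + p(r−1)].

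- p = 0.1, r = 1.25: 0.025/1.025 = 2.4%, about 0.5 mg of 20 mg
- p = 0.2, r = 1.25: 0.05/1.05 = 4.8%, about 1.0 mg
- p = 0.2, r = 1.5: 0.10/1.10 = 9.1%, about 1.8 mg
- p = 0.3, r = 1.5: 0.15/1.15 = 13.0%, about 2.6 mg

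**4. Plausibility against the plan's SD**

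Take 20 mg and SD 5.2 (variance 27.04) as describing the mixed population. The difference between strata is d = 20(r−1) / [1 + p(r−1)], and the between-stratum variance is p(1−p)d².

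- p = 0.1, r = 1.25: d = 4.9, variance 2.1, 8% of the total
- p = 0.2, r = 1.25: d = 4.8, variance 3.6, 13%
- p = 0.2, r = 1.5: d = 9.1, variance 13.2, 49%
- p = 0.3, r = 1.5: d = 8.7, variance 15.9, 59%

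The last two would need psychiatric status alone to explain about half or more of all variation in opioid use. I keep only the first two: 0.5-1.0 mg.

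**5. Effect on the non-inferiority test**

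This is a normal approximation for means, although the planned test is Wilcoxon. With 27 per group, SE = 5.2 × √(2/27) = 1.415 mg. For a selection shift b in QLB minus TEA, power at true equality is Φ((4−b)/SE − 1.96), and the false non-inferiority rate at a true difference of 4 mg is Φ(−b/SE − 1.96).

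| b (mg) | Power | False non-inferiority |
|---|---|---|
| −1 | 0.94 | 0.105 |
| 0 | 0.81 | 0.025 |
| +0.5 | 0.70 | 0.010 |
| +1 | 0.56 | 0.004 |

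The psychiatric illustration lies on the positive side. The documents do not say on which side the language and consent items would fall.

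**The case against.** The strongest case against has five parts.

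*Uncontrolled* may govern the whole TEA line. Treated, controlled depression would then not exclude a TEA patient. The missing clause concerns study assessments that chart-review patients never undergo, so its absence may simply reflect the data source. This stands. A reader might infer that any psychiatric disorder excludes a TEA patient, but the text does not settle that. It does leave two readings, and on the narrower one the TEA line still has no interference test.

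The consent and language exclusions come with prospective enrolment, where subjects must consent, answer pinprick questions and keep a diary. The primary outcome is drawn from medication records in hospital. This explains the difference but does not remove it. It does mean that no direction or size can be claimed for these items.

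The contraindication exclusions are nearly redundant for TEA patients, who had to receive an epidural and the regimen. This stands, and I place no weight on those items.

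The psychiatric bias, if present, is conservative for QLB. This stands for that item: it would cost power and would lower the false non-inferiority rate.

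A stratum found only in QLB need not be lost to analysis. If psychiatric history is recorded, those patients could be set aside in a restricted comparison. That is true, but no such analysis is planned.

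**Conclusion.** The point holds as a mismatch in stated eligibility that may make the cohorts differ by selection. It does not show that they do. The TEA psychiatric criterion is broader or ambiguous, language and consent exclusions apply to QLB only, and the TEA opioid-use limit lacks a usable date. The planned tests correct for none of this.

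The only size that can be offered is an illustration for the psychiatric item: about 0.5-1.0 mg of the 4 mg margin, with power at true equality falling from 0.81 to about 0.70-0.56. It rests on the broad reading, an assumed prevalence of 10-20%, an assumed 25% higher opioid use, complete removal from TEA and complete retention in QLB. A reader might extend it to 1.8-2.6 mg by assuming 50% higher use, but that fits poorly with the plan's own SD. The net direction across all items cannot be obtained from the documents. The change is worth making because it costs little and removes a choice from the chart screener, not because a bias of known size has been shown.

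**What to change.** - Use one psychiatric exclusion, worded identically for both cohorts and verifiable from a chart: for example, a disorder that is uncontrolled or is documented as impairing assessment or cooperation.
- Apply the English-language exclusion to the TEA chart search, and exclude incapacity where the chart documents it. Capacity will not always be recoverable from a past record, so the rule should cover documented cases only.
- Date the TEA opioid-use limit to the preoperative assessment.
- List pregnancy and the block and multimodal-agent contraindications for TEA for consistency. The contraindication items should change little, given the TEA inclusion criteria.
- Report the number of charts screened and excluded, by reason, beside the QLB screening counts.

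The cost is a minor rewording of the criteria and the chart-screening form, and a slightly smaller or different TEA screening pool. No extra patients or procedures are needed, and the sample-size calculation is unchanged.
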